E3.1. Secondary Aim#1: Determine whether prehospital tranexamic acid as compared to placebo reduces the incidence of hyperfibrinolysis (estimated percent lysis > 7.5%), acute traumatic coagulopathy (ATC, presenting INR > 1.4), improves PT measurements and additional r-TEG parameters, D-dimer levels, activated Protein C levels, and plasmin-antiplasmin complexes.

Secondary Hypothesis 1: Prehospital tranexamic acid as compared to placebo will reduce the incidence hyperfibrinolysis (estimated percent lysis > 7.5%), reduce the incidence of patients with an arrival INR > 1.4, improve PT and additional presenting r-TEG parameters of coagulopathy including ACT, r-value, k-time, α -angle, maximal amplitude (MA) and G-values and D-dimer levels, activated Protein C levels and plasmin-antiplasmin complexes.

E.3.2. Secondary Aim#2: Determine whether prehospital tranexamic acid as compared to placebo results in a lower incidence of 24 hour mortality, acute lung injury, multiple organ failure, nosocomial infection, early seizures, pulmonary embolism, shock parameters and early resuscitation and transfusion requirements.

Secondary Hypothesis 2A: Prehospital tranexamic acid as compared to placebo will reduce the incidence of 24 hour and 30 day mortality, acute lung injury, multiple organ failure, nosocomial infection, early (24hr) seizures and in-hospital pulmonary embolism.

Secondary Hypothesis 2B: Prehospital tranexamic acid as compared to placebo will improve presenting base deficit, 24 hour crystalloid requirements and reduce 6 hour and 24 hour blood and blood component transfusion requirements (PRBC, FFP and platelets).

E.3.3. Secondary Aim #3: To investigate potential novel mechanisms by which tranexamic acid alters the inflammatory response to injury independent of effects on hyperfibrinolysis. Investigations of the effects of tranexamic acid on inflammation will include analysis of platelet and leukocyte activation via flow cytometry, measurements of plasmin levels and subsequent plasmin mediated complement activation and the early inflammatory cytokine response to trauma.

Secondary Hypothesis 3A: Prehospital tranexamic acid as compared to placebo will reduce plasmin levels and markers of platelet and leukocyte activation measured by flow cytometry (FACS) and result in a plasmin mediated reduction of complement activation as measured by C3a and Factor B levels.

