hospital and prehospital clinical trials. All enrolling centers and respective investigators similarly have busy emergency medical services and significant experience with multi-center trials, the research infrastructure to allow them to successfully occur and have no other clinical investigations that would preclude participation in the current proposal. *Participating Institutions include: University of Pittsburgh, University of Arizona, University of Texas at San Antonio, and the University of Utah. The University of Tennessee at Memphis will be utilized as an alternate/additional site if required.*

H.2. Study Population: The study population will include blunt or penetrating injured patients at risk of hemorrhage being transported via emergency medical services from the scene of injury or from referring hospital to a definitive trauma center that is participating in the trial. We have selected similar inclusion criteria as the prior large, prospective study⁴¹ (CRASH-2). This represents a similar level of acuity than the CRASH-2 study and additionally allows the mechanism of tranexamic acid's benefit to be characterized across a spectrum of injury severity since the pre-specified analysis of the CRASH-2 trial demonstrated that the mortality benefit attributable to early tranexamic acid remained consistent across patients with low thru high predicted mortality, suggesting its use should not be limited to the most severely injured.⁴⁴ The study group may also contain traumatic brain injured patients who represent a subgroup that may also benefit from early tranexamic intervention.⁴⁵ Based upon our own current data (2011-2012) in injured patients that require air medical transport, these inclusion criteria are associated with over a 65% blood transfusion rate in the first 24 hours from admission and represents the most pertinent population for the trial.

H.2.1. Specific Inclusion Criteria:

1. Blunt or penetrating injured patients at risk of hemorrhage being transported via emergency medical services from the scene of injury or from referring hospital to a definitive trauma center that is participating in the trial

AND

2. Within 2 hours of estimated time of injury

AND

3A. Hypotension (Systolic Blood Pressure (SBP) < 90mmHg)

i. At scene of injury or during emergency medical transport

ii. Documented at referring hospital prior to emergency medical transport arrival

OR

3B. Tachycardia (heart rate >110 beats per minute)

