H.5.1. *Prehospital Phase Randomization:* Individual patients meeting criteria while en route via emergency medical transport will be randomized using an allocation sequence block size of 8 to either 1 gram of tranexamic acid or placebo diluted in 100cc of normal saline given over approximately 10 minutes. A single prehospital treatment box containing ascending numerically labeled (1-8) treatment packs (randomized with a computer random number generator) will be distributed to each respective helicopter base (or station in the case of ground ambulance). In an ascending numerical order fashion treatment packs will be utilized for enrolled patients. The box and treatment pack # will be recorded by research staff upon arrival for all randomized patients. The patient and all treatment and research staff will be blinded to the treatment arm. All intervention vials will be covered to obscure view of vial contents to prehospital staff giving the intervention and amber colored syringes will be utilized to maintain blinding. IDS at the University of Pittsburgh will be unblinded to the prehospital intervention. Additionally, the pharmacy at each respective participating center will have access to the prehospital randomization/assignment scheme once the prehospital intervention box and treatment # are provided to them by the accepting research staff at each participating center.

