I.4.4. Multiple organ failure: Organ dysfunction will be evaluated via a well-validated scoring system referred to as the Denver Postinjury Multiple Organ Failure Score.⁹¹⁻⁹³ Patients who are never admitted to the ICU or those with a length of ICU stay of less than 48 hrs will be considered to have a Denver score of 0. A summary of the Denver score may be calculated by summing the worst scores of each of the individual systems over the course of the ICU stay. A summary Denver score > 3 will be classified as multiple organ failure (MOF). Scores will be determined daily up until post injury day 30 or ICU discharge. All time variables to the respective outcome event will be determined from the day of initial injury, for time-to-event analysis and multivariate Cox proportional hazard regression analysis.

I.4.5. Early seizures: Seizures will be prospectively monitored for over the first 24 hours from injury. Whether the seizures occurred post-operatively or in those patients who did not require operative intervention will be documented. Neurology consultation will be sought in those patients with seizure activity. Classification of seizure type and management will be based upon formal neurology consultation. Repeat occurrence and outcomes associated with seizure will similarly be documented.

I.4.6. In-hospital pulmonary embolism: Pulmonary embolism that occurs during the primary admission hospital stay will be documented for all enrolled patients. Radiographic confirmation via CT imaging, transthoracic or trans-esophageal echo, or ventilation/perfusion scanning will be required.

I.4.7. Blood and blood component transfusion and resuscitation requirements: 6 and 24-hour transfusion requirements for blood, fresh frozen plasma and platelet transfusion will be determined by recording the number of units transfused for each component from the time of trauma bay arrival. Transfusion components which are initiated will be considered transfused irrespective of completion. Similar determinations for crystalloid requirements (volume in cc's) over the first 24hrs of injury will occur.

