J.4. Predefined Subgroup Analyses: Predefined subset analyses will be performed looking at 1.) patients who ultimately did or did not required blood transfusion 2.) those patients with significant traumatic brain injury (Head AIS >2) versus those without significant brain injury (Head AIS ≤ 2), 3.) those patients enrolled from the scene of injury versus those enrolled from a referral hospital, 4.) those patients that require operative intervention in the first 24 hours, 5.) those patients with a preinjury history of vitamin K antagonist medication history versus those without, 6.) those patients with preinjury history of antiplatelet medication history. 7.) those patients who ultimately did or did not require massive transfusion (≥ 10 units blood in first 24hrs). It is recognized that the study is not appropriately powered for these subgroup comparisons and the results and conclusions formulated from these subgroup analyses will be considered exploratory in nature and will not be used as a basis for treatment recommendations.

J.5. Randomization of Ineligible Subjects: It is anticipated that there will be a small proportion of patients enrolled who receive either tranexamic acid or placebo that in retrospect will not have met the entry criteria and are thus ineligible. In this circumstance, patients will be analyzed according to the group to which they were randomized. Subgroup analyses based on eligibility criteria will be performed if the number of patients so affected is large. However, based on the relatively limited inclusion and exclusion criteria it is anticipated that the frequency of this event will be low.

J.6. Non-adherence: In some circumstances, patients may receive the incorrect treatment packet. Non-adherence is most likely to occur in the case of the exsanguinating patient when time is limited and the wrong treatment pack is utilized. Fortunately, this event is relatively rare. In keeping with the intention-to-treat analytic design, these patients will be analyzed with the group to which they were to be randomized to.

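### J.4 subgroups 1, 4 and 7 are formed mainly after randomisation, two of them by a variable TXA is expected to change; J.4 does not say so and nothing keeps them out of the DSMB's subgroup-consistency review

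*Combined protocol and SAP*

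**What the plan says.** Section J.4 lists seven predefined subgroups. Three depend on events after hospital arrival:

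- Subgroup 1: "patients who ultimately did or did not required blood transfusion", with no time window.
- Subgroup 7: "those patients who ultimately did or did not require massive transfusion", defined as 10 or more units in 24 hours.
- Subgroup 4: "those patients that require operative intervention in the first 24 hours".

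The timing is set elsewhere. In H.5.1, "Individual patients meeting criteria while en route via emergency medical transport will be randomized". I.4.7 measures transfusion by "recording the number of units transfused for each component from the time of trauma bay arrival". Section N.2 also records blood given at the scene or the referring hospital, so some transfusion can precede randomisation.

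Transfusion is itself a trial outcome (I.2). Secondary Hypothesis 2B in E.3.2 states that TXA will "reduce 6 hour and 24 hour blood and blood component transfusion requirements".

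J.4 puts one caveat on all seven subgroups: they are underpowered and exploratory, and "will not be used as a basis for treatment recommendations".

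For the DSMB, P.1 includes a priori subgroups specified elsewhere in the protocol among what is monitored. P.4 and Appendix 4 (opening paragraph and section 4) make consistency of effects across subgroups one of the inputs to a recommendation. None of these sections says which subgroups are meant.

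**The concern.** Randomisation balances the arms in the whole trial and within strata fixed beforehand. If TXA changes who is transfused, the transfused patients on TXA are a different selection from the transfused patients on placebo, and the same holds for the non-transfused. A mortality difference within a stratum then mixes any treatment effect with a difference in severity. More patients would not remove this, so a caveat about power does not address it.

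The link is direct for subgroup 7, which is a threshold on 24-hour units. For subgroup 1 it is a short inference, because Hypothesis 2B speaks of requirements and I.4.7 counts units, so the number of patients who would move between some blood and none is unknown. Subgroup 4 is also formed after randomisation, though no document hypothesises a TXA effect on operation.

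Two readings are exposed. In the report, classification alone could make TXA look more or less effective in a stratum than it is. At the interim looks, the same artefact could enter the DSMB's judgement of whether effects are consistent. J.4's bar on treatment recommendations does not mention stopping recommendations.

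**Working it through.** **The plan's own figure.** J.4 states no number. As background, the power in P.4 reproduces. With 497 per arm, 10% v 16%, pooled proportion 0.13 and two-sided alpha 0.05:

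- z = [0.06 − 1.96 × √(2 × 0.13 × 0.87 / 497)] / √[(0.10 × 0.90 + 0.16 × 0.84) / 497] = (0.06 − 0.0418) / 0.0212 = 0.86
- power = 0.804, against the stated 80%.

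**Inputs for the bias.**

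- From H.2: "these inclusion criteria are associated with over a 65% blood transfusion rate in the first 24 hours from admission" (65% used).
- From K.1: 16% control mortality.
- Assumed: severity S is standard normal; the logits of transfusion and of death each rise with S at slope b, from 0.5 to 2.0; transfusion and death are independent given S; TXA cuts the transfusion rate by a relative 2% to 20%.
- Intercepts are set to reproduce 65% and 16%. TXA has **no effect on death** unless stated.

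Two ways of reducing transfusion were tried:

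- *Common-logit*: the transfusion intercept falls, so patients near the margin are spared most.
- *Equal averting*: every transfusion has the same chance of being averted.

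**One case by hand** (equal averting, b = 2.0, 10% cut). The model gives control mortality of 22.61% in the transfused and 3.72% in the non-transfused. TXA moves 6.5% of patients, with 22.61% mortality, into the non-transfused stratum:

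- TXA non-transfused mortality = (35 × 3.72 + 6.5 × 22.61) / 41.5 = 6.68%
- spurious difference = 6.68 − 3.72 = +2.96 points
- SE at 497 per arm = √(0.0668 × 0.9332 / 206.3 + 0.0372 × 0.9628 / 174) = 2.25 points, so the bias is 1.31 SE.

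**Spurious mortality difference, TXA minus placebo, in points, over b = 0.5 to 2.0:**

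| Relative change in transfusion rate | Common-logit, transfused | Common-logit, non-transfused | Equal averting, non-transfused |
|---|---|---|---|
| none | 0 | 0 | 0 |
| 2% cut | +0.04 to +0.3 | +0.04 to +0.1 | +0.1 to +0.7 |
| 5% cut | +0.1 to +0.8 | +0.1 to +0.3 | +0.3 to +1.6 |
| 10% cut | +0.2 to +1.7 | +0.2 to +0.6 | +0.5 to +3.0 |
| 20% cut | +0.4 to +3.5 | +0.4 to +1.3 | +0.8 to +5.1 |
| 10% increase | −0.2 to −1.5 | −0.2 to −0.6 | not run |

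Under equal averting the bias in the transfused is 0.

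**Largest bias in SE units (b = 2.0), at the two interim looks and at full enrolment:**

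| Case | 166 per arm | 332 per arm | 497 per arm |
|---|---|---|---|
| Transfused, common-logit, 20% cut | 0.57 | 0.80 | 0.98 |
| Non-transfused, common-logit, 20% cut | 0.37 | 0.52 | 0.64 |
| Non-transfused, equal averting, 10% cut | 0.76 | 1.07 | 1.31 |
| Non-transfused, equal averting, 20% cut | 1.27 | 1.79 | 2.20 |

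**With the design effect on death (16% v 10%).** With no cut, the relative risk (RR) is 0.63 to 0.64 in the transfused and 0.51 to 0.62 in the non-transfused.

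- Common-logit, 10% to 20% cut: RR 0.60 to 0.75 across both strata.
- Equal averting: the transfused RR stays at 0.63 to 0.64. The non-transfused RR is 0.64 to 1.03 (10% cut) or 0.66 to 1.42 (20% cut).
- RR exceeds 1 only at b = 2.0, where the control stratum has about 174 × 3.72% = 6.5 deaths.

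**A second method** fixes three groups (always, avoidably and never transfused), with overall mortality 16% and no TXA effect on death. The group mortalities are assumed, and transfusion is avoided in 5, 10 or 15% of all patients.

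- Always and avoidably transfused both at 22%: never-transfused mortality is (0.16 − 0.65 × 0.22) / 0.35 = 4.9%. Non-transfused mortality on TXA is 7.0, 8.7 or 10.0% (odds ratio 1.47, 1.86, 2.18).
- Always 23%, avoidable 5%: the odds ratio is 1.08, 1.18 or 1.29 in the transfused and 0.99, 0.91 or 0.82 in the non-transfused.

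**Massive transfusion** (control rate 5% to 15% assumed, 20% cut, common-logit): from under +0.1 to +2.7 points in the massively transfused, at most 0.31 SE. Subgroup 4 was not quantified.

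**The case against.** The strongest reply has five parts.

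- **Size.** No document supports a 10% to 20% cut. Section C.6 reports no difference in total transfusion in the cited large randomised trial, and greater 24-hour requirements with TXA in the retrospective military study. With no change there is no bias. At b = 1.0 and a 10% cut, the full-enrolment bias is only 0.21 SE (transfused, common-logit) and 0.15 or 0.45 SE (non-transfused, common-logit or equal averting). At the interim looks it is smaller still. *This stands, and it limits the size.*
- **Reversal.** An apparent reversal needs the steepest slope, equal averting and at least a 10% cut, and rests on very few deaths. *This stands.*
- **Model.** Transfusion and death are taken as independent given severity, although early death can preclude transfusion. The 65% comes from air-medical patients over 24 hours, while the trial also enrols from ground ambulances and subgroup 1 has no time window. *This stands: the figures illustrate and do not predict.*
- **DSMB.** No section names subgroups 1, 4 or 7 for its use, the charter lists tables for overall endpoints, and Appendix 4 Tables 5 and 6 show no such strata. The DSMB includes a biostatistician and an epidemiologist and treats the stopping rule as a guideline. *This shows that use is permitted, not required. It does not show that use is excluded, and P.1 refers to subgroups specified in the protocol.*
- **Existing caveat.** The results are already exploratory. *True, but the caveat treats all seven subgroups alike and does not tell a reader which are protected by randomisation.*

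J.4 also names no outcome. Reading these as mortality comparisons is an inference from 30-day mortality being the primary endpoint.

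**Conclusion.** The concern holds. Subgroups 1 and 7 condition mainly on what happens after randomisation, and the plan itself expects TXA to change that variable. Subgroup 4 is post-randomisation without a hypothesised effect. J.4 does not disclose this, and P.1, P.4 and Appendix 4 do not keep these strata out of the consistency review.

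The size and direction cannot be settled from the documents. Under the stated assumptions the bias in subgroup 1 runs from negligible (2% cut) to about 3 points (10% cut) or 5 points (20% cut) in the non-transfused. It is zero if transfusion does not change, and under common-logit it reverses sign if transfusion rises by 10%. In subgroup 7 it is at most about 0.3 SE in the scheme run, which does not model survival long enough to receive 10 units. The defect is structural and does not depend on any one figure.

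The primary intention-to-treat analysis, its power and the formal boundary on pooled 30-day mortality are not affected. This should be changed, but it does not threaten the main result.

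**What to change.** In J.4, state that subgroups 1, 4 and 7 are formed after randomisation, will be reported descriptively, and do not estimate causal treatment effects.

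In P.1, P.4 and Appendix 4, limit the DSMB's subgroup-consistency check to the J.4 subgroups fixed before the prehospital infusion (scene v referral hospital, vitamin K antagonist history, antiplatelet history) or reflecting the initial injury (Head AIS).

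The cost is wording in those four places, with no new data and no new analyses. The descriptive results stay available. What is given up is any claim to a causal effect in transfused or operated patients, which these subgroups could not support.
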